5.1 Definitions

5.1.1 Adverse Events (AE)

An adverse event (AE) is defined as any reaction, side effect, or untoward event that occurs during the clinical trial associated with the use of a test article in humans, whether or not the event is considered related to the treatment or clinically significant. For this study, AEs will include events reported by the patient, as well as clinically significant abnormal findings on physical examination or laboratory evaluation. A new illness, symptom, sign or worsening of a pre-existing condition or abnormality is considered an AE. An abnormal laboratory value will be considered an AE if the laboratory abnormality is characterized by any of the following:

- Results in discontinuation from the study
- Is associated with clinical signs or symptoms
- Requires treatment or any other therapeutic intervention
- Is associated with death or another serious adverse event, including hospitalization.
- Is judged by the Investigator to be of significant clinical impact

All AEs, including clinically significant abnormal findings on laboratory evaluations, regardless of severity, will be followed until satisfactory resolution.

5.1.2 Suspected Adverse Reaction

Suspected adverse reaction means any adverse event for which there is a reasonable possibility that the test article caused the adverse event. For the purposes of IND safety reporting, "reasonable possibility" means there is evidence to suggest a causal relationship between the test article and the adverse event. A suspected adverse reaction implies less certainty about causality than adverse reaction, which means any adverse event caused by a test article.

5.1.3 Serious Unexpected Adverse Reaction (SUSAR)

An adverse event or suspected adverse reaction is considered "unexpected" if it is not listed in the investigator brochure or is not listed at the specificity or severity that has been observed; or, if an investigator brochure is not required or available, is not consistent with the risk information described in the general investigational plan or elsewhere in the current application. "Unexpected" also refers to adverse events or suspected adverse reactions that are mentioned in the investigator brochure as occurring with a class of the test article or as anticipated from the pharmacological properties of the drug but are not specifically mentioned as occurring with the test article under investigation.

5.1.4 Serious Adverse Event (SAE)

An adverse event or suspected adverse reaction is considered serious if in the view of the investigator or the sponsor, it results in any of the following:

- Death within 30 days of Descartes-11 infusion
- Grade 4 or 5 CRS, infusion reaction, neurotoxicity
- Inpatient hospitalization or prolongation of existing hospitalization (except for protocol-mandated ~24-hour admission for observation due to new-onset fever)
- Persistent or significant incapacity or substantial disruption of the ability to conduct normal life functions
- A congenital anomaly/birth defect
- Important medical events that may not result in death, be life-threatening, or require hospitalization may be considered a SAE experience when, based upon appropriate medical judgment, they may jeopardize the patient or subject and may require medical or surgical intervention to prevent one of the outcomes listed in this definition.

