5.2.4 Recording of Adverse Events

At each contact with the subject during the adverse event recording period (defined in [Section 5.2.1](#)), the investigator must seek information on adverse events by specific questioning and, as appropriate, by examination. Information on all adverse events should be recorded immediately in the source document, and in the appropriate adverse event module of the case report form (CRF). All clearly related signs, symptoms, and abnormal diagnostic procedures results should be recorded in the source document, though should be grouped under one diagnosis. To the extent possible, adverse events should be recorded as a diagnosis and symptoms used to make the diagnosis recorded within the diagnosis event. Do not list symptoms if a diagnosis can be assigned.

Conditions that were already present at the time of informed consent should be recorded in the Medical History CRF. Any condition listed in a subject's medical history for which the severity increases at the time of, or post-Descartes-11 infusion, should be captured as an adverse event.

Adverse events (including lab abnormalities that constitute AEs) should be described using a diagnosis whenever possible, rather than individual underlying signs and symptoms. When a clear diagnosis cannot be identified, each sign or symptom should be reported as a separate Adverse Event. The clinical course of each event should be followed until resolution, stabilization, or until

it has been determined that the study treatment or participation is not the cause. As detailed as possible, each adverse event should be evaluated to determine:

- The severity grade (CTCAE Version 5.0 Grade 1-5)
- Its duration (start and end dates)
- Its relationship to the study treatment: Is there a reasonable possibility that the AE is related to Descartes-11- No (unrelated) or Yes. If yes- is the event definitely, probably, possibly or unlikely related to the investigational treatment (Descartes-11).
- Action taken with respect to study or investigational treatment (none, dose adjusted, temporarily interrupted, permanently discontinued, unknown, not applicable)
- Whether medication or therapy taken (i.e., no concomitant medication/non-drug therapy, concomitant medication/non-drug therapy)
- Whether it is serious, as defined in [Section 5.1](#).

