5.2.5 SAE and SUSAR Reporting

To ensure patient safety, every SAE and SUSAR, regardless of suspected causality, occurring during the adverse event reporting period defined in [Section 5.2.1](#) must be reported to the Sponsor within 24 hours of learning of its occurrence. Recurrent episodes, complications, or progression of the initial SAE must be reported as follow-up information is received. An SAE occurring at a different time interval or otherwise considered completely unrelated to a previously reported one should be reported separately as a new event.

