5.2.5.3 FDA Notification by the Study Sponsor

The Sponsor is required to report certain study events in an expedited fashion to the FDA. These written notifications of adverse events are referred to as IND safety reports. The sponsor must report an IND safety report as described in:

<http://www.fda.gov/downloads/Drugs/GuidanceComplianceRegulatoryInformation/Guidances/UCM227351.pdf>

The following describes the safety reporting requirements by timeline for reporting and associated type of event:

- **Within 7 Calendar Days** any study event that is unexpected, fatal or life-threatening suspected adverse reaction.
- **Within 15 Calendar Days** any study event that is unexpected, suspected adverse reaction that is serious, but not fatal or life-threatening -or- a previous adverse event that was not initially deemed reportable but is later found to fit the criteria for reporting, any finding from tests in laboratory animals that suggest a significant risk for human subjects including reports of mutagenicity, teratogenicity, or carcinogenicity or reports of significant organ toxicity at or near the expected human exposure.

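### Section 5.1.4 has no general life-threatening criterion, so a life-threatening event outside three named toxicities, with no countable admission, can be handled as an ordinary AE

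*Combined protocol and SAP*

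**What the plan says.** Section 5.1.4 of the protocol lists six ways for an event to be serious:

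1. "Death within 30 days of Descartes-11 infusion".
2. "Grade 4 or 5 CRS, infusion reaction, neurotoxicity".
3. "Inpatient hospitalization or prolongation of existing hospitalization (except for protocol-mandated ~24-hour admission for observation due to new-onset fever").
4. Lasting or significant incapacity.
5. Congenital anomaly.
6. A judgement clause, which begins "Important medical events that may not result in death, be life-threatening, or require hospitalization may be considered a SAE experience when" and applies where, in medical judgement, "they may jeopardize the patient or subject and may require medical or surgical intervention to prevent one of the outcomes listed in this definition".

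The rest of the reporting chain depends on that list:

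- **Seriousness test (5.2.4).** Each AE is assessed for "Whether it is serious, as defined in" Section 5.1.
- **Site to sponsor, expedited (5.2.5 and 5.2.5.1).** Every SAE and SUSAR "must be reported to the Sponsor within 24 hours of learning of its occurrence".
- **Site to sponsor, ordinary (5.2.4).** An AE is entered in the eCRF within 10 working days of the site learning of it.
- **Sponsor to FDA (5.2.5.3).** The 7-calendar-day report covers "any study event that is unexpected, fatal or life-threatening suspected adverse reaction".
- **Pause rule (5.5).** Among other triggers, the study pauses when two subjects have Grade 4 vital-organ events judged probably or definitely related, within 14 days after the last infusion. The study team then meets within 24 hours of the event.

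**The concern.** The FDA trigger uses a category that the investigator's definition lacks. In 5.1.4 the term life-threatening appears only in the judgement clause, which is framed for events that need not be life-threatening and says only that they may be counted as serious. Among the mandatory criteria, severity counts for CRS, infusion reaction and neurotoxicity alone.

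The protocol itself foresees Grade 4 events of other kinds. Section 4.5.1 names Grade 4 tumor lysis syndrome, Grade 4 organ-function laboratory values and Grade 4 cytopenias when it sets out exceptions to removal from therapy. If such an event is life-threatening and the site applies 5.1.4 literally, it may be recorded as non-serious. The sponsor cannot assess, report or act on an event that it has not yet received. At stake are the timeliness of an expedited safety report and of the safety review that 5.5 relies on, for a cell product given six times in 18 days.

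**Working it through.** No sample-size, power or error-rate figure bears on this point, and the plan gives no figure to reproduce. The check sets the passages side by side and counts days.

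**Step 1: which routes bring a life-threatening event to the sponsor in 24 hours?** Take an event that is not CRS, infusion reaction or neurotoxicity and that is not fatal or incapacitating.

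| Route | Mandatory? | Does it reach the event? |
|---|---|---|
| Grade 4 or 5 bullet (5.1.4) | Yes | No; three named toxicities only |
| Hospitalization bullet (5.1.4) | Yes | Only if it causes or prolongs an admission that counts |
| Important medical event (5.1.4) | No | It can, at the investigator's judgement |
| SUSAR (5.1.3, 5.2.5) | Unclear | Only if unexpected; the text defines unexpected, and seriousness comes from the heading and hence 5.1.4 |

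**Step 2: can such an event lack a countable admission?** The protocol leaves three openings.

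- Section 3.3.3 lets the investigator discharge a patient after the two-hour observation, so treatment is largely outpatient.
- Sections 5.1.4 and 5.2.2 exclude the roughly 24-hour fever-observation stay. An event during that stay that does not lengthen it is not counted through hospitalization.
- Section 5.2.2 excludes admissions for treatment of the myeloma itself, unless there is clinical worsening or admissions become more frequent. The SAE period runs to 30 days after the last infusion (5.2.1), which on schedule is Day 18 + 30 = Day 48. Section 3.4 allows transplant after the Day 28 assessment. An inpatient transplant stay can therefore fall inside the SAE window without itself counting.

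**Step 3: the lag.** Inputs: 24 hours (5.2.5), 10 working days (5.2.4) and 7 calendar days (5.2.5.3).

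- Ten working days counted from the day after a weekday of knowledge span two weekends: 10 + 4 = 14 calendar days. If the site learns of the event at a weekend, the span is 12 or 13 days. If the day of knowledge counts as day 1, it can be as short as 11. Public holidays are ignored.
- Extra delay against the 24-hour route, at the maximum: 14 − 1 = 13 days.

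**Step 4: the 7-day report.** The documents do not say when its clock starts, so both cases are shown.

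- Clock starts when the site learns of the event: entry at the limit alone overruns by 11 − 7 = 4 to 14 − 7 = 7 days.
- Clock starts when the sponsor is informed: the deadline can still be met, but the clock itself starts up to 11 to 14 days after the site knew.

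**Step 5: the pause rule.** It counts Grade 4 vital-organ events, a category that overlaps with life-threatening events but is not the same. Notice may be late for those that are life-threatening and follow the ordinary route. A life-threatening criterion would bring those forward; it would not guarantee 24-hour notice of every event that the rule counts.

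**The case against.** The strongest reply is that a miss needs several things at once. The event must be outside the three named toxicities, must neither cause nor prolong a countable admission, must not be judged an important medical event, and must not be sent in as a SUSAR. The hospitalization bullet covers any event type, and Appendix A recommends admission for suspected CRS or fever and ICU transfer on deterioration. Most life-threatening events would be admitted, and many investigators would report the rest from habit. All of this stands, and it makes the gap narrow. It does not close it, because the remaining routes rest on discretion or on an ambiguous definition.

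Three stronger readings are tempting, and the documents do not support them.

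- *A reader might infer that the important-medical-event clause cannot apply, because life-threatening is not a listed outcome.* Death and hospitalization are listed, and a life-threatening event may well need intervention to prevent one of them. The permissive opening of the clause does not exclude such events. Its weakness is that it is optional.
- *A reader might infer that the 24-hour duty rests on the SAE definition alone.* It also covers SUSARs, and the body of 5.1.3 turns only on unexpectedness. A literal reader could use that route for precisely the unexpected reactions that 5.2.5.3 concerns. The heading's word for serious leads back to 5.1.4, so the route is unreliable, but it is not absent.
- *A reader might infer that the FDA deadline will be missed by about a week, since 14 days is twice 7.* That compares a limit for site entry with a sponsor clock whose start is not given, and it uses the maximum lag.

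Nor do the documents indicate that any particular event, such as tumor lysis or arrhythmia, would be managed without admission.

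**Conclusion.** Wrong as written, in a limited form. Section 5.1.4 has no stand-alone life-threatening criterion, although 5.2.5.3 uses that category as a trigger. A life-threatening, non-fatal, non-incapacitating event outside the three named toxicities and without a countable admission meets no mandatory criterion. It can properly be handled as an ordinary AE, with up to about 14 calendar days to entry instead of 24 hours.

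The documents give no basis for estimating how often this would happen; it is likely to be uncommon. The conclusion assumes that sites apply 5.1.4 as the only definition of serious, as 5.2.4 directs. A missed 7-day deadline is conditional on when that clock starts; a delayed report is not. The effect on the 5.5 pause review is confined to those Grade 4 vital-organ events that are also life-threatening. The primary endpoint, eligibility and sample size are untouched.

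**What to change.** Add one bullet to 5.1.4 and to the SAE form: *Life-threatening adverse event (any type)*, matched to the wording of 5.2.5.3. Keep the bullet on Grade 4 or 5 CRS, infusion reaction and neurotoxicity. Word the new bullet by threat to life and not by grade, so that a Grade 4 laboratory value does not become an SAE automatically.

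Reconcile the SAE list in Appendix B (4.1.4) at the same time. It also lacks a life-threatening criterion, and it names neither death nor hospitalization, although Appendix B 4.2.2 treats admissions as SAEs.

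The cost is one line in each list, a form update and a few more expedited reports. No dose, treatment or clinical rule changes.

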5.1.5 Protocol Deviation

A one-time, unintentional action or process that departs from the IRB-approved study protocol, involving one incident and identified retrospectively, after the event occurred. Any leukapheresis-related failure or deviation will be recorded, even if it does not constitute a per-protocol AE.

5.2 Recording of Adverse Events

5.2.1 Adverse Event Recording Period

The study period during which adverse events must be reported is normally defined as the period from the initiation of any study procedures to the protocol therapy completion. For this study, collection of adverse events will begin with enrollment until the subject is off-study. Serious Adverse Event reporting period starts with leukapheresis and ends at 30 days after last Descartes-11 infusion.

All unresolved adverse events should be followed by the investigator until the events are resolved, the subject is lost to follow-up, or the adverse event is otherwise explained. At the last scheduled visit, the investigator should instruct each subject to report any suspected adverse event(s) that might reasonably be related to participation in this study. The investigator should notify the Sponsor of any death or adverse event occurring at any time after a subject has discontinued or terminated study participation if the event may reasonably be related to this study. The Sponsor should also be notified if the investigator should become aware of the development of cancer or of a congenital anomaly in a subsequently conceived offspring of a subject that has participated in this study.

5.2.2 Hospitalization, Prolonged Hospitalization or Surgery

Any adverse event that results in hospitalization or prolonged hospitalization should be documented and reported as a serious adverse event unless specifically instructed otherwise as

below. Any condition responsible for surgery should be documented as an adverse event if the condition meets the criteria for an adverse event. Neither the condition, hospitalization, prolonged hospitalization, nor surgery are reported as an adverse event in the following circumstances:

- Hospitalization or prolonged hospitalization for diagnostic or elective surgical procedures for a preexisting condition. Surgery should not be reported as an outcome of an adverse event if the purpose of the surgery was elective or diagnostic and the outcome was uneventful.
- Hospitalization or prolonged hospitalization for therapy of the target disease of the study, unless there is clinical worsening or an increase in frequency of hospital admissions as judged by the clinical investigator.
- Hospitalization for protocol-mandated 24-hour observation following new onset of fever following infusion of Descartes-11.

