The potency of virally transduced CAR therapies comes with significant risks. All clinical trials of virally transduced CAR T-cells have recorded serious instances of cytokine release syndrome (CRS) and neurological toxicity. In the recent American Society of Blood and Marrow Transplant (ASBMT) consensus meeting, CRS was defined as “a supraphysiologic response following any immune therapy that results in the activation or engagement of endogenous or infused T cells and/or other immune effector cells. Symptoms can be progressive, must include fever at the onset, and may include hypotension, capillary leak (hypoxia) and end organ dysfunction.”⁴¹ CRS is a prototypical systemic inflammatory response syndrome that occurs hours to days after CAR T-cell infusion. Signs and symptoms include fever, myalgia, malaise, and, in more severe cases, a capillary leak syndrome associated with hypoxia, hypotension, and occasionally renal dysfunction and coagulopathy. Peak CAR T-cells as a result of *in vivo* proliferation has been strongly associated with the severity of CRS in many CAR T-cell studies.^{42,43} The proliferation of CAR T-cells upon engagement with target antigen drives them to secrete cytokines that initiates a cascade of systemic inflammatory events. Among all cytokines elevated during CRS, IL-6 plays a central role as neutralization of this cytokine quickly and effectively reverses clinical deterioration in most cases.

The first presenting symptom of CRS is usually fever associated with mild constitutional symptoms.^{42,44-46} In a number of patients, the initial mild symptoms progress over the course of hours to days and turn into a systemic inflammatory syndrome characterized by sinus tachycardia, hypotension and hypoxia. In severe cases, patients may require mechanical ventilation and vasopressors. CRS can start as early as the day of CAR T-cell infusion and in most cases it occurs within the first 14 days following the infusion. Severe cases appear to occur closer to the time of infusion and the severity of CRS was reported to correlate with peak CAR T-cell levels as mentioned above as well as disease burden^{42,43} and addition of preconditioning chemotherapy.^{43,44,46,47}

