Appendix A MANAGEMENT GUIDELINES FOR CAR T-CELL-RELATED TOXICITIES

The clinical signs and symptoms of CAR T-related toxicities guide the grading and management of CRS and neurotoxicity. This protocol adapts management recommendations described by Lee et al.⁴¹ A copy of this reference will be provided to the investigator and staff are encouraged to review it prior to enrolling the first patient. The following is recommended:

1. All patients with suspicion of CRS or fever above 37.9°C should be admitted for at least a 24-hour observation.
2. Infectious disease work-up with blood cultures should be initiated each time CRS is suspected. Empiric broad-spectrum intravenous antibiotics are recommended.
3. Vital signs should be checked at least every 4 hours with strict urine input and output monitoring.
4. Patients with poor oral intake should be started on intravenous fluids. Patients with 80% of their baseline systolic blood pressure (or if systolic BP<90mmHg) should be given a 0.5-1 L fluid bolus. Fluid boluses can be repeated as needed; however, they should be kept to a minimum with a low threshold of starting low dose vasopressor as the capillary leak during CRS can lead to fluid overload.
5. Patients should be transferred to the Intensive Care Unit (ICU) if:
 - a. the patient's systolic pressure does not respond to the first fluid bolus;
 - b. the patient requires 2 or more fluid boluses within 24 hours;
 - c. the patient's heart rate remains above 125/min for at least 4 hours;
 - d. the patient's supplemental oxygen requirement is more than 40% FiO₂; or
 - e. the patient has >Grade 2 neurotoxicity.
6. Patients admitted to the ICU should have the following:
 - a. vital signs checked every 2 hours;
 - b. cardiac enzymes, ECG and echocardiogram evaluation;
 - c. if systolic blood pressure is below 75% of baseline or below 85 mmHg, norepinephrine should be started;
 - d. CBC should be checked twice a day and cytopenias should be treated as follows:
 - i. blood transfusion to keep Hgb above 8.0 g/dL;
 - ii. platelet transfusion to keep platelet above 20k;
 - iii. growth factors for neutropenia can be started if ANC is below 1000/µL. Filgrastim is recommended due to a shorter half-life compared with pegfilgrastim.
7. Tocilizumab at the FDA-approved dose for CRS should be administered in the following circumstances:
 - a. grade 3 CRS;
 - b. grade 2 CRS that is not resolving within 72 hours; or
 - grade 2 CRS in the context of other co-morbidities or old age.

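### Section 5.2.2, read literally, exempts a post-infusion fever managed with the 24-hour observation stay from being reported as an adverse event at all, contradicting Sections 5.1.1, 5.1.4, 5.2.1 and 5.2.4

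*Combined protocol and SAP*

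**What the plan says.** Section 5.2.2 begins with a general rule that an AE leading to hospitalization is reported as an SAE unless the section says otherwise. It then introduces its exceptions: "Neither the condition, hospitalization, prolonged hospitalization, nor surgery are reported as an adverse event in the following circumstances". The third exception reads: "Hospitalization for protocol-mandated 24-hour observation following new onset of fever following infusion of Descartes-11".

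Other sections treat the same event differently:

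- **Section 5.1.4** lists inpatient hospitalization as a criterion of seriousness, "except for protocol-mandated ~24-hour admission for observation due to new-onset fever". Only the admission is exempt, and only from making the event serious.
- **Section 5.1.1** defines an AE broadly: "A new illness, symptom, sign or worsening of a pre-existing condition or abnormality is considered an AE". It makes no exception for fever.
- **Section 5.2.1** collects AEs from enrollment until the subject goes off study.
- **Section 5.2.4** states: "Information on all adverse events should be recorded immediately in the source document, and in the appropriate adverse event module". Each event is to be given a grade, start and end dates and a causality assessment.

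Two further places link fever to CRS. The consensus definition quoted in Section 1.2.5 says of CRS: "Symptoms can be progressive, must include fever at the onset". Appendix A, item 1, says: "All patients with suspicion of CRS or fever above 37.9°C should be admitted for at least a 24-hour observation".

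**The concern.** The first two exceptions in Section 5.2.2 concern a pre-existing condition and the target disease. Not reporting the condition makes sense there, because it did not arise from study treatment. The third exception is different: the condition is new and follows the study drug. Carrying the same lead-in over to it tells the site not to report a possible reaction to the product.

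What is at stake is the AE count for the reactions of most interest with this product. Section 1.2.6 argues that mRNA transfection sharply limits CRS and neurotoxicity, and Section 3.3.4 says neither has been seen with Descartes-11. Fever is required at the onset of CRS, so the exempted circumstance is where mild CRS would first appear. A rule that lets those events go unreported can only lower the count used to judge that argument. The primary endpoint, MRD-negative sCR at Day 28, is not affected.

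**Working it through.** No arithmetic applies, and the plan gives no figure to reproduce. The check is to set the passages side by side.

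1. **Does the lead-in govern the fever item?** Yes. The fever stay is the third of three items under one introductory sentence, with no separate wording of its own.

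2. **What does the lead-in exempt, and at what level?** It names the condition as well as the hospitalization, and it operates at AE level. For the fever item the only candidate for the condition is the new fever.

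3. **Does the lead-in suit this item?** Section 4.2.2 of Appendix B, the cell collection protocol, uses the same lead-in with only the first two items. The fever item appears only in the treatment protocol, and it is the only one where the exempted condition is a new event after study drug. This suggests that an item was added to a general list without the lead-in being adjusted.

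4. **What do the other sections require for the same fever?**

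| Section | Fever itself | 24-hour admission |
|---|---|---|
| 5.2.2, literal reading | Not reported as an AE | Not reported as an AE |
| 5.1.1 | An AE (new sign or symptom) | Not addressed |
| 5.1.4 | Not exempted | Does not make the event serious |
| 5.2.1 | Collected if an AE | Not addressed |
| 5.2.4 | Entered in the CRF with grade, dates and causality | Not addressed |

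The first row conflicts with the others on the fever. Section 5.2.4 also asks for each sign or symptom to be reported separately when there is no clear diagnosis, which is exactly the case of an isolated fever.

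5. **Who falls into the exempted circumstance?** Section 3.3.4.1 and Appendix A both lead to admission for a temperature above 37.9°C. The exemption reaches those whose stay is the 24-hour observation for new fever. Appendix A asks for at least that long, and item 10 holds patients recovering from CRS until they have had no fever for a further day. A recognised CRS admission will therefore usually outlast the exemption and come under the general SAE rule. What remains exposed is mainly the short fever, including mild CRS with fever as its only sign.

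6. **Is there another route to the count?** Section 4.5.1 excepts fever of any grade from the toxicities that end treatment. The pause rules in Section 5.5 count attributed deaths and Grade 4 events in vital organs. Neither would ordinarily register a short fever, so in the text available the AE record is the route by which it would reach a safety table.

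A related inconsistency bears on the scope: Sections 5.1.4 and 5.2.2 call the admission mandated, while Section 3.3.4 and Appendix A present their guidance as recommendations.

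**The case against.** The best defence is that the intent is plain and narrow. Section 5.2.2 opens as a rule about SAE reporting, its third item names only the hospitalization, and Section 5.1.4 waives only the seriousness of the admission. Elsewhere AEs are defined and collected broadly, CRS is graded by ASTCT criteria (Section 3.3.4.4), and fever is treated as a toxicity (Section 4.5.1). A sensible site would record the fever. This makes it likely that the authors meant only to waive SAE status. It does not remove the conflict: Section 5.2.2 is the specific instruction and Section 5.1.1 the general one, so two sites could handle the same fever differently and each point to the protocol. Nor does a distinction between reporting and recording help, since Section 5.2.4 uses both words for AEs.

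Three stronger inferences are tempting, and the documents do not support them.

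- **That fever-only CRS vanishes from the safety record.** The protocol nowhere says CRS goes unreported, and Section 5.2.4 asks for a diagnosis where one can be made. Longer stays are outside the exemption. Vital signs, concomitant medications and AE history are taken at every infusion visit (Section 4.1.2). The risk is to the AE counts, under a literal reading.
- **That an early signal is hidden between infusions.** Patients must tell the study team of a temperature above 37.9°C (Section 3.3.3), and each infusion requires a temperature below 37.9°C and no sign of infection (Section 3.3.1.2). The treating team would know. Non-serious AEs may be entered up to 10 working days later (Section 5.2.4), so recording the fever would not ensure that the medical monitor saw it before an infusion 3 to 4 days on.
- **That the bias can be sized.** One could note that 0 events in 34 patients gives a one-sided 95% upper limit of 1 − 0.05^(1/34) = 8.4%, and set an assumed true rate beside it. A count of zero would need every site to read Section 5.2.2 literally for every event and every fever to settle within the stay. The documents give no fever rate for Descartes-11, so the calculation measures nothing about this trial.

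Some text is also out of view. The secondary and exploratory objectives are unreadable, the CRS biomarker section is redacted, and Section 6 leaves the analysis to a separate SAP. Whether a fever or CRS rate is a formal endpoint, or is captured by another route, cannot be settled.

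**Conclusion.** The contradiction is real and should be corrected. On its literal wording, Section 5.2.2 exempts a new post-infusion fever from AE reporting when it is managed with the 24-hour observation stay, against Sections 5.1.1, 5.1.4, 5.2.1 and 5.2.4. Omission is a risk that depends on how sites read the section, not a certainty. If fevers are omitted, the error goes one way: febrile-reaction and low-grade CRS rates come out too low. Its size cannot be estimated, because the documents give neither a fever rate nor any indication of how sites apply the rule. The conclusion rests on two assumptions: that the lead-in applies to the third item as printed, and that no CRF instruction or other document outside those available overrides it.

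**What to change.** Reconcile the passages within Section 5.2.2. Take the third item out from under the present lead-in, or reword it, so that it exempts only the 24-hour admission, and only from SAE reporting, in line with Section 5.1.4. Add a sentence that the fever, or CRS with its ASTCT grade if criteria are met, is still recorded as an AE with grade, dates and causality. The same edit should reconcile the description of the admission as mandated with the recommendation status given in Section 3.3.4.

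The cost is a sentence or two of protocol wording, a few more AE records, and possibly a higher reported fever or CRS rate. No dose, schedule or clinical management changes. It is best done before enrollment, since grade and causality are hard to reconstruct afterwards.
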